### 3.2.1.2 Urinalysis

Analysis Set:	Safety Analysis Set
Analysis Variable(s):	
 
Protein [-, +-, 1+, 2+, 3+, 4+]
 
Glucose [-, 1+, 2+, 3+, 4+, 5+]
 
Blood [-, +-, 1+, 2+, 3+]
 
Ketone Body [-, +-, 1+, 2+, 3+, 4+]
 

Visit:	Baseline (prior to TVP-1012 administration), Week 3, Week 6, Week 14, Week 20, Week 26, Week 29, Week 32, Week 40, Week 46, Week 52
Analysis Method(s):	The following summaries will be provided for each treatment group in the preceding study.
	
 
(1) A shift table for baseline (prior to TVP-1012 administration) and each visit after administration (Week 3 to Week 52) will be provided.
 

## 3.2.2 Vital Signs, Physical Findings, and Other Observations Related to Safety

### 3.2.2.1 Vital Signs

Analysis Set:	Safety Analysis Set
Analysis Variable(s):	
 
Body temperature
 
Systolic blood pressure
 
Diastolic blood pressure
 
Pulse rate
 

Visit:	Baseline (prior to TVP-1012 administration), Week 3, Week 6, Week 10, Week 14, Week 20, Week 26, Week 29, Week 32, Week 36, Week 40, Week 46, Week 52
Analysis Method(s):	
The following summaries will be provided for each treatment group in the preceding study.
 
If a vital sign parameter has both lower and upper MAV criteria, analysis will be performed for each. Definitions of parameters subject to this analysis and MAV criteria are given in Appendix 2 of this Statistical Analysis Plan.
 
 
(1) Descriptive statistics for observed values for each visit and changes (each visit after administration [Week 3 to Week 52] - baseline [prior to TVP-1012 administration]) will be provided.
 
(2) Case Plots
 
(3) Overall frequency distributions of MAV after the administration of TVP-1012 will be provided.
 

### **3.2.2.2 12-Lead ECG**

Analysis Set: Safety Analysis Set

Analysis Variable(s): Heart Rate  
RR Interval  
PR Interval  
QT Interval  
QRS Interval  
QTcB Interval  
QTcF Interval

12-Lead ECG Interpretation [Within Normal Limits, Abnormal but Not Clinically Significant, Abnormal and Clinically Significant]

Visit: Baseline (prior to TVP-1012 administration), Week 14, Week 26, Week 40, Week 52

Analysis Method(s): For each variable other than 12-lead ECG interpretations, summaries (1) and (2) will be provided by treatment group in the preceding study.  
For 12-lead ECG interpretation, summary (3) will be provided by treatment group in the preceding study.

- (1) Descriptive statistics for observed values for each visit and changes (each visit after administration (Week 14 to Week 52)-baseline (prior to TVP-1012 administration) will be provided.
- (2) Case Plots
- (3) A shift table for baseline (prior to TVP-1012 administration) and each visit after administration will be provided.

### **3.2.2.3 Weight**

Analysis Set: Safety Analysis Set

Analysis Variable(s): Weight

Visit: Baseline (prior to TVP-1012 administration), Week 14, Week 26, Week 40, Week 52

Analysis Method(s): The following summaries will be provided for each treatment group in the preceding study.

- (1) Descriptive statistics for observed values for each visit and changes (each visit after administration (Week 14 to Week 52)-baseline (prior to TVP-1012 administration) will be provided.
- (2) Case Plots

**4 Significance Level and Confidence Coefficient**

- Confidence coefficient: 95% (two-sided)

**Creation History (version management)**

Version	Date	Created/Modified by	Comments
1	2016.09.30	[REDACTED]	Creation of first version
2	2017.04.11	[REDACTED]	Creation of second version

**[Appendix 1] A Comparison Table for Changes in TVP-1012/OCT-001**Amendment from First Version (Created on 30 September 2016) to Second Version (Created on 11 April 2017)

Page	Existing Text	Revised Text	Rationale for Amendment
22	
3.1.3 Examination of Subgroups for Treatment-Emergent Adverse Event
 
Stratified Variable(s):
 
Smoking history
 
[Yes, No]
 
Timing of Study Drug Administration
 
[Before breakfast, After breakfast]
	
3.1.3 Examination of Subgroups for Treatment-Emergent Adverse Event
 
Stratified Variable(s):
 
Age (years)
 
[Min<= - <65, 65<= - <=Max]
 
Gender
 
[Male, Female]
 
Smoking history
 
[Yes, No]
 
Timing of Study Drug Administration
 
[Before breakfast, After breakfast]
	Modified after examining it with related functional departments.

**[Appendix 2]      Definition of MAV Criteria****(1) MAV Criteria****1) Vital Signs**

For each test item, those obtained until 7 days after the administration of TVP-1012 (including 7 days after the end of TVP-1012 administration and evaluable data [i.e., non-missing and acceptable according to the Handling Rules for Analysis Data]) will be subject and the determination on MAV will be conducted according to the following table. The LLN and ULN in the following table will be the lower limit and upper limit of reference values within the normal range of each test item.

Vital Signs

Test item	Gender	Age	MAV Criteria	
			Lower	Upper
Body Temperature (°C)	-	-	<35.6	>37.7
Systolic Blood Pressure (mmHg)	-	-	<90	>180
Diastolic Blood Pressure (mmHg)	-	-	<50	>100
Pulse Rate (bpm)	-	-	<45	>120

Overall determination after administration of TVP-1012

The presence or absence of MAV for each subject will be determined for each test item according to the rules (1) to (3). If a test item has both lower and upper MAV criteria, analysis will be performed for each.

- [1] If it is determined that at least 1 item among the evaluable data after the administration of TVP-1012 “meets the MAV Criteria,” it will be determined as “Yes.”
- [2] If it does not correspond to [1] and it is determined that at least 1 item among the evaluable data after the administration of TVP-1012 “does not meet the MAV Criteria,” it will be determined as “No.”
- [3] If it corresponds to neither [1] nor [2], it will be excluded from the analysis for the results of the determination.

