6.2.3 Justification for Dose Regimen

[REDACTED]

In the preceding study, 1 mg of TVP-1012 or placebo was administered for 26 weeks to evaluate the efficacy and safety of TVP-1012 1 mg.

In this study, the dose of 1 mg of TVP-1012 will be maintained for subjects treated with 1 mg of TVP-1012 in the preceding study, to evaluate administration at 1 mg for 52 weeks. In addition, subjects treated with placebo in the preceding study will be switched to 1 mg of TVP-1012 in this study, to evaluate administration at 1 mg for 26 weeks, for the purpose of evaluating a large number of subjects as much as possible.

[REDACTED]

CONFIDENTIAL

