## Vital Signs

Visit	Scheduled Study Time	Visit Windows	
		Number of days after administration	Number of days after the end of administration
Baseline (prior to TVP-1012 administration)	Number of days after administration: -1	-22 ~ -1	
Week 3	Number of days after administration: 21	1 ~ 31	< 8
Week 6	Number of days after administration: 42	32 ~ 55	< 8
Week 10	Number of days after administration: 70	56 ~ 83	< 8
Week 14	Number of days after administration: 98	84 ~ 118	< 8
Week 20	Number of days after administration: 140	119 ~ 160	< 8
Week 26	Number of days after administration: 182	161 ~ 192	< 8
Week 29	Number of days after administration: 203	193 ~ 213	< 8
Week 32	Number of days after administration: 224	214 ~ 237	< 8
Week 36	Number of days after administration: 252	238 ~ 265	< 8
Week 40	Number of days after administration: 280	266 ~ 300	< 8
Week 46	Number of days after administration: 322	301 ~ 342	< 8
Week 52	Number of days after administration: 364	343 ~ 385	< 8

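### The vital-sign MAV table counts any on-drug reading past a cut-off without regard to baseline, and gives one overall frequency per group although the groups have up to 12 and up to 6 scheduled on-drug visits

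*SAP*

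**What the plan says.** SAP 3.2.2.1 plans three outputs for vital signs: (1) observed values and changes from baseline at each visit, (2) case plots, and (3) the MAV table: "Overall frequency distributions of MAV after the administration of TVP-1012 will be provided". The layout is by randomized group: "The following summaries will be provided for each treatment group in the preceding study".

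SAP Appendix 2 sets the classification.

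- Rule [1]: a subject is *Yes* for an item if "at least 1 item among the evaluable data after the administration of TVP-1012" meets the criterion.
- Rule [2]: a subject not caught by [1], with at least one evaluable reading that does not meet the criterion, is *No*.
- Rule [3]: "If it corresponds to neither [1] nor [2], it will be excluded from the analysis for the results of the determination". This removes subjects with no evaluable on-drug reading. It is not a baseline exclusion.
- The eligible readings run on, "including 7 days after the end of TVP-1012 administration and evaluable data". No common time limit is set for the two groups.

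The visits after baseline are "Week 3, Week 6, Week 10, Week 14, Week 20, Week 26, Week 29, Week 32, Week 36, Week 40, Week 46, Week 52". These are counted from the first TVP-1012 dose. Under the SAP Glossary that is the first treatment-period dose of the preceding study for 1 mg->1 mg, and the first extension dose for P->1 mg. Protocol 6.2.3 explains why: "subjects treated with placebo in the preceding study will be switched to 1 mg of TVP-1012 in this study". Protocol 8.1.3 starts extension dosing on the day after VISIT 8, so the Week 26 reading is baseline for P->1 mg.

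**The concern.** The MAV table is the only cut-off-based summary of vital signs, which are a secondary safety endpoint. It has two weaknesses.

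First, a subject beyond a cut-off before the first TVP-1012 dose, and again on any later visit, is counted in the same way as a subject who crosses it for the first time on drug. Nothing else planned for vital signs counts new crossings. Hematology, serum chemistry, urinalysis and ECG interpretation each have a shift table from baseline (SAP 3.2.1.1, 3.2.1.2, 3.2.2.2). Vital signs do not.

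Second, the chance of ever having one reading past a cut-off grows with the number of readings, and the longer-treated group has more of them. For adverse events over time, SAP 3.1.2 handles unequal exposure with onset intervals and interval-specific denominators. It has nothing comparable for MAV. A reader comparing the two columns could take a difference in observation time for a drug effect.

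**Working it through.** The plan states no MAV rate, so there is no figure of its own to reproduce. The visit counts come from the documents. The risks are assumptions.

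**Visit counts.** SAP 3.2.2.1 lists 12 visits after baseline. P->1 mg contributes only the extension visits in Protocol Appendix A: Weeks 29, 32, 36, 40, 46 and 52. Subtracting 26 gives on-drug Weeks 3, 6, 10, 14, 20 and 26, which is 6 visits. Both counts are scheduled maxima; unscheduled evaluable readings would also count.

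**Full attendance, independent visits.** Let p be the per-visit chance of a reading past the cut-off, the same in both groups (no drug effect). Then P(*Yes*) = 1 − (1 − p)^k, with k = 12 or 6.

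| p (assumed) | 1 mg->1 mg, k = 12 | P->1 mg, k = 6 | Ratio |
|---|---|---|---|
| 0.2% | 2.4% | 1.2% | 1.99 |
| 0.5% | 5.8% | 3.0% | 1.97 |
| 1% | 11.4% | 5.9% | 1.94 |
| 2% | 21.5% | 11.4% | 1.89 |
| 5% | 46.0% | 26.5% | 1.74 |

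**Planned dropout.** The safety analysis set is everyone with at least one TVP-1012 dose (Protocol 13.1.1), so it includes 1 mg subjects who stopped in the preceding study. Protocol 13.3 gives 120 randomized per group, 182 entering the extension, 155 treated for 26 weeks and 59 for 52 weeks. The split by group is inferred: 182/2 = 91 enter from each group, and 155 − 91 = 64 P->1 mg subjects reach 26 on-drug weeks. Losses are taken as linear between these points.

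- The six on-drug weeks sum to 3 + 6 + 10 + 14 + 20 + 26 = 79.
- 1 mg->1 mg, first six visits: 6 − (79 × 29/26)/120 = 5.27.
- 1 mg->1 mg, last six visits: 6 × 91/120 − (79 × 32/26)/120 = 3.74. The total is 9.0 visits per subject.
- P->1 mg: 6 − (79 × 27/26)/91 = 5.1 visits per subject.

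With r_k the fraction still attending at visit k, P(*Yes*) = Σ r_k · p(1 − p)^(k−1). At p = 1% this gives 8.6% vs 5.0%, a ratio of 1.72. Over p = 0.2% to 5% the ratio runs from 1.76 to 1.57.

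**Within-subject correlation.** Suppose a share b of subjects is habitually beyond a cut-off, including at baseline, with repeat chance q per visit, and the rest have p = 1%. Then P(*Yes*) = b[1 − (1 − q)^k] + (1 − b)[1 − 0.99^k], here at full attendance.

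- b = 2%, q = 30%: 13.1% vs 7.5%, ratio 1.75.
- b = 10%, q = 50%: 20.2% vs 15.1%, ratio 1.34.

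Across b = 2% to 10% and q = 30% to 50%, subjects already beyond the cut-off at baseline make up 15% to 49% of the *Yes* count in 1 mg->1 mg and 24% to 65% in P->1 mg.

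**Common window.** With both groups limited to the first 26 on-drug weeks, planned dropout at p = 1% gives 5.1% vs 5.0%, a ratio of 1.03.

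**The case against.** The table is descriptive. No test, between-group estimate or decision rule is attached to vital signs; the SAP's only between-group estimate is for MDS-UPDRS (2.1.1.2). The columns carry the group labels, exposure is tabulated by group (SAP 1.3.1), and Protocol 6.2.3 says the groups serve 52-week and 26-week evaluation. By-visit statistics on the TVP-1012 clock line the groups up at equal exposure through Week 26, and they include minima and maxima. Case plots are added. Protocol 13.1.4 reserves shift tables for categorical variables, and vital signs are continuous, so their absence is no departure from the protocol. MAV itself is an SAP addition that the protocol does not require. Unfavorable signs can also be recorded as adverse events, with rules for pre-existing conditions (Protocol 10.1.2, 10.1.3).

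Most of this stands, and it limits the harm. It does not remove the point. Neither the by-visit statistics nor the case plots report how many subjects newly crossed a cut-off, and adverse-event recording depends on investigator judgement.

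A reader might go further and infer that the longer-treated group will show about twice the MAV frequency. The documents do not support that. It needs full attendance, independent visits and a small per-visit risk, whereas the planned numbers imply substantial dropout. The baseline weakness itself supposes habitual abnormality, which is correlation, and correlation shrinks the visit-count effect.

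**Conclusion.** The point holds as a weakness of one descriptive table. The MAV row cannot distinguish new from pre-existing abnormalities, and its 1 mg->1 mg frequency will tend to exceed the P->1 mg frequency with no drug effect.

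At an assumed 1% per-visit risk, the ratio is at most 1.94 and about 1.72 under planned dropout. With 2% to 10% of subjects habitually beyond a cut-off it is about 1.75 to 1.34 at full attendance. Dropout and correlation were worked separately; together they would bring the ratio below 1.72. All of these rest on a per-visit risk, repeat chances and a dropout split by group that the documents do not give.

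Three broader inferences are not supported:

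- that baseline is ignored for vital signs altogether: it is used in the change-from-baseline summaries, and only the MAV classification omits it;
- that counting any single reading is a faulty definition: it is workable, and the fault is pairing it with unequal observation and no baseline condition;
- that the plan leads to a wrong test or a formal claim of cumulative toxicity: no such comparison is planned.

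The Handling Rules for Analysis Data are not among the documents. Appendix 2 cites them only to define evaluable data.

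**What to change.** Keep rule [1]. In SAP 3.2.2.1(3) and Appendix 2:

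1. Show each MAV row by whether the same criterion was met at Baseline prior to TVP-1012, and report treatment-emergent MAV among subjects who did not meet it there.
2. Report MAV for the first 26 weeks on TVP-1012 in both groups, and separately for the full 52 weeks in 1 mg->1 mg.

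The cost is SAP wording and a longer table, with a slightly smaller denominator for the treatment-emergent row. No new data are needed, because the baseline window and the visit schedule already exist.

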**[Appendix 3] MDS-UPDRS Score**

- MDS-UPDRS individual score

Part I

Number	Variable	Score
1.1	Cognitive impairment	(0, 1, 2, 3, 4, UR)
1.2	Hallucinations and psychosis	(0, 1, 2, 3, 4, UR)
1.3	Depressed mood	(0, 1, 2, 3, 4, UR)
1.4	Anxious mood	(0, 1, 2, 3, 4, UR)
1.5	Apathy	(0, 1, 2, 3, 4, UR)
1.6	Features of DDS	(0, 1, 2, 3, 4, UR)
1.7	Sleep problems	(0, 1, 2, 3, 4)
1.8	Daytime sleepiness	(0, 1, 2, 3, 4)
1.9	Pain and other sensations	(0, 1, 2, 3, 4)
1.10	Urinary problems	(0, 1, 2, 3, 4)
1.11	Constipation problems	(0, 1, 2, 3, 4)
1.12	Light headedness on standing	(0, 1, 2, 3, 4)
1.13	Fatigue	(0, 1, 2, 3, 4)

Part II

Number	Variable	Score
2.1	Speech	(0, 1, 2, 3, 4)
2.2	Saliva and drooling	(0, 1, 2, 3, 4)
2.3	Chewing and swallowing	(0, 1, 2, 3, 4)
2.4	Eating tasks	(0, 1, 2, 3, 4)
2.5	Dressing	(0, 1, 2, 3, 4)
2.6	Hygiene	(0, 1, 2, 3, 4)
2.7	Handwriting	(0, 1, 2, 3, 4)
2.8	Doing hobbies and other activities	(0, 1, 2, 3, 4)
2.9	Turning in bed	(0, 1, 2, 3, 4)
2.10	Tremor	(0, 1, 2, 3, 4)
2.11	Getting out of bed, a car, or a deep chair	(0, 1, 2, 3, 4)
2.12	Walking and balance	(0, 1, 2, 3, 4)
2.13	Freezing	(0, 1, 2, 3, 4)

## Part III

Number	Variable	Score
3.1	Speech	(0, 1, 2, 3, 4, UR)
3.2	Facial expression	(0, 1, 2, 3, 4, UR)
3.3a	Rigidity-Neck	(0, 1, 2, 3, 4, UR)
3.3b	Rigidity-RUE	(0, 1, 2, 3, 4, UR)
3.3c	Rigidity-LUE	(0, 1, 2, 3, 4, UR)
3.3d	Rigidity-RLE	(0, 1, 2, 3, 4, UR)
3.3e	Rigidity-LLE	(0, 1, 2, 3, 4, UR)
3.4a	Finger tapping-Right hand	(0, 1, 2, 3, 4, UR)
3.4b	Finger tapping-Left hand	(0, 1, 2, 3, 4, UR)
3.5a	Hand movements-Right hand	(0, 1, 2, 3, 4, UR)
3.5b	Hand movements-Left hand	(0, 1, 2, 3, 4, UR)
3.6a	Pronation-supination movements-Right hand	(0, 1, 2, 3, 4, UR)
3.6b	Pronation-supination movements-Left hand	(0, 1, 2, 3, 4, UR)
3.7a	Toe tapping-Right foot	(0, 1, 2, 3, 4, UR)
3.7b	Toe tapping-Left foot	(0, 1, 2, 3, 4, UR)
3.8a	Leg agility-Right leg	(0, 1, 2, 3, 4, UR)
3.8b	Leg agility-Left leg	(0, 1, 2, 3, 4, UR)
3.9	Arising from chair	(0, 1, 2, 3, 4, UR)
3.10	Gait	(0, 1, 2, 3, 4, UR)
3.11	Freezing of gait	(0, 1, 2, 3, 4, UR)
3.12	Postural stability	(0, 1, 2, 3, 4, UR)
3.13	Posture	(0, 1, 2, 3, 4, UR)
3.14	Global spontaneity of movement	(0, 1, 2, 3, 4, UR)
3.15a	Postural tremor-Right hand	(0, 1, 2, 3, 4, UR)
3.15b	Postural tremor-Left hand	(0, 1, 2, 3, 4, UR)
3.16a	Kinetic tremor-Right hand	(0, 1, 2, 3, 4, UR)
3.16b	Kinetic tremor-Left hand	(0, 1, 2, 3, 4, UR)
3.17a	Rest tremor amplitude-RUE	(0, 1, 2, 3, 4, UR)
3.17b	Rest tremor amplitude-LUE	(0, 1, 2, 3, 4, UR)
3.17c	Rest tremor amplitude-RLE	(0, 1, 2, 3, 4, UR)
3.17d	Rest tremor amplitude-LLE	(0, 1, 2, 3, 4, UR)
3.17e	Rest tremor amplitude-Lip/jaw	(0, 1, 2, 3, 4, UR)
3.18	Constancy of rest tremor	(0, 1, 2, 3, 4, UR)

## Part IV

Number	Variable	Score
4.1	Time spent with dyskinesias	(0, 1, 2, 3, 4)
4.2	Functional impact of dyskinesias	(0, 1, 2, 3, 4)
4.3	Time spent in the OFF state	(0, 1, 2, 3, 4)
4.4	Functional impact of fluctuations	(0, 1, 2, 3, 4)
4.5	Complexity of motor fluctuations	(0, 1, 2, 3, 4)
4.6	Painful OFF-state dystonia	(0, 1, 2, 3, 4)

0: Normal, 1: Slight, 2: Mild, 3: Moderate, 4: Severe, UR: Unable to Rate

- Each total score based on scores of each MDS-UPDRS variable

The score will be calculated according to the following rules for evaluable data (i.e., non-missing and acceptable according to the Handling Rules for Analysis Data).

MDS-UPDRS Part I total score:	Total of variable 1.1 to variable 1.13
MDS-UPDRS Part II total score:	Total of variable 2.1 to variable 2.13
MDS-UPDRS Part III total score:	Total of variable 3.1 to variable 3.18
MDS-UPDRS Part IV total score:	Total of variable 4.1 to variable 4.6
MDS-UPDRS Part II + Part III total score:	Total of variable 2.1 to variable 2.13 and variable 3.1 to variable 3.18
MDS-UPDRS tremor score:	Total of variable 2.10, variable 3.15a to variable 3.18
MDS-UPDRS muscle rigidity score:	Total of variable 3.3a to variable 3.3e
MDS-UPDRS bradykinesia score:	Total of variable 3.4a to variable 3.8b and variable 3.14

- \* The score will be calculated using the variable on the same day of the assessment.
- \* If a missing or “UR” value is contained in the variable used for calculation, the score will not be calculated.

**[Appendix 4]      Modified Hoehn and Yahr Scale**

- Each Severity Classification of Modified Hoehn and Yahr Scale

The score that corresponds to each severity classification will be used according to the following table.

Severity Classification	Variable	Score
Stage 0	No Parkinsonism	0
Stage 1	Unilateral Parkinsonism	1
Stage 1.5	Unilateral Parkinsonism and axial involvement	1.5
Stage 2	Bilateral Parkinsonism without impairment of balance	2
Stage 2.5	Mild bilateral Parkinsonism with recovery on retropulsion (pull) test	2.5
Stage 3	Mild to moderate Parkinsonism with impairment of balance but physically independent	3
Stage 4	Severe Parkinsonism; still able to walk or stand unassisted	4
Stage 5	Wheelchair bound or bedridden unless aided	5

**[Appendix 5] PDQ-39 Score****• PDQ-39 individual score**

Number	Variable	Score
1	Had difficulty doing the leisure activities which you would like to do?	(0, 1, 2, 3, 4)
2	Had difficulty looking after your home, e.g. DIY, housework, cooking?	(0, 1, 2, 3, 4)
3	Had difficulty carrying bags of shopping?	(0, 1, 2, 3, 4)
4	Had problems walking half a mile?	(0, 1, 2, 3, 4)
5	Had problems walking 100 yards?	(0, 1, 2, 3, 4)
6	Had problems getting around the house as easily as you would like?	(0, 1, 2, 3, 4)
7	Had difficulty getting around in public?	(0, 1, 2, 3, 4)
8	Needed someone else to accompany you when you went out?	(0, 1, 2, 3, 4)
9	Felt frightened or worried about falling over in public?	(0, 1, 2, 3, 4)
10	Been confined to the house more than you would like?	(0, 1, 2, 3, 4)
11	Had difficulty washing yourself?	(0, 1, 2, 3, 4)
12	Had difficulty dressing yourself?	(0, 1, 2, 3, 4)
13	Had problems doing up your shoe laces?	(0, 1, 2, 3, 4)
14	Had problems writing clearly?	(0, 1, 2, 3, 4)
15	Had difficulty cutting up your food?	(0, 1, 2, 3, 4)
16	Had difficulty holding a drink without spilling it?	(0, 1, 2, 3, 4)
17	Felt depressed?	(0, 1, 2, 3, 4)
18	Felt isolated and lonely?	(0, 1, 2, 3, 4)
19	Felt weepy or tearful?	(0, 1, 2, 3, 4)
20	Felt angry or bitter?	(0, 1, 2, 3, 4)
21	Felt anxious?	(0, 1, 2, 3, 4)
22	Felt worried about your future?	(0, 1, 2, 3, 4)
23	Felt you had to conceal your Parkinson's from people?	(0, 1, 2, 3, 4)
24	Avoided situations which involve eating or drinking in public?	(0, 1, 2, 3, 4)
25	Felt embarrassed in public due to having Parkinson's disease?	(0, 1, 2, 3, 4)

26	Felt worried by other people's reaction to you?	(0, 1, 2, 3, 4)
27	Had problems with your close personal relationships?	(0, 1, 2, 3, 4)
28	Lacked support in the ways you need from your spouse or partner?	(0, 1, 2, 3, 4, 5)
29	Lacked support in the ways you need from your family or close friends?	(0, 1, 2, 3, 4)
30	Unexpectedly fallen asleep during the day?	(0, 1, 2, 3, 4)
31	Had problems with your concentration, e.g. when reading or watching TV?	(0, 1, 2, 3, 4)
32	Felt your memory was bad?	(0, 1, 2, 3, 4)
33	Had distressing dreams or hallucinations?	(0, 1, 2, 3, 4)
34	Had difficulty with your speech?	(0, 1, 2, 3, 4)
35	Felt unable to communicate with people properly?	(0, 1, 2, 3, 4)
36	Felt ignored by people?	(0, 1, 2, 3, 4)
37	Had painful muscle cramps or spasms?	(0, 1, 2, 3, 4)
38	Had aches and pains in your joints or body?	(0, 1, 2, 3, 4)
39	Felt unpleasantly hot or cold?	(0, 1, 2, 3, 4)

0: Never, 1: Occasionally, 2: Sometimes, 3: Often, 4: Always (or cannot do at all), 5: If you do not have a spouse or partner tick here.

- PDQ-39 score by domain (rounded to the first decimal place)

The score will be calculated according to the following rules for evaluable data (i.e., non-missing and acceptable according to the Handling Rules for Analysis Data).

Mobility:  $(\text{Total of variable 1 to variable 10}) / (4 \times 10) \times 100$

Activities of daily living:  $(\text{Total of variable 11 to variable 16}) / (4 \times 6) \times 100$

Emotional well-being:  $(\text{Total of variable 17 to variable 22}) / (4 \times 6) \times 100$

Stigma:  $(\text{Total of variable 23 to variable 26}) / (4 \times 4) \times 100$

Social support:

[In the case when variable 28 is other than 5]  $(\text{Total of variable 27 to variable 29}) / (4 \times 3) \times 100$

[In the case when variable 28 is 5]  $(\text{Total of variables 27 and 29}) / (4 \times 2) \times 100$

Cognitions:  $(\text{Total of variable 30 to variable 33}) / (4 \times 4) \times 100$

Communication:  $(\text{Total of variable 34 to variable 36}) / (4 \times 3) \times 100$

Bodily discomfort:  $(\text{Total of variable 37 to variable 39}) / (4 \times 3) \times 100$

\* The score will be calculated using the variable on the same day of the assessment.

\* If a missing value is contained in the variable used for calculation, the score will not be calculated.

- PDQ-39 Summary Index (rounded to the first decimal place)

The score will be calculated according to the following rules for evaluable data (i.e., non-missing and acceptable according to the Handling Rules for Analysis Data).

(Total of PDQ-39 Score by Domain Mobility-Bodily discomfort) / 8

- \* The score will be calculated using the variable on the same day of the assessment.
- \* If a missing value is contained in the variable used for calculation, the score will not be calculated.
